6.2.2 Enrollment, Baseline, and/or Randomization

Enrollment

Enrollment is defined as the date of randomization at which point all eligibility criteria are confirmed and the individual has agreed to participate; this is recorded on a case-report form. AEs will be collected after the participant is enrolled. Participants will be told to contact study staff and/or providers about any health related changes they experience. See Safety Assessments and the DSMP for additional details.

Baseline Assessments

For participants who have successfully been screened for eligibility and are enrolled into the study, baseline assessments are performed against which to measure the study outcome. These will also ensure the groups are balanced with respect to baseline characteristics.

Primary and secondary outcomes will be measured using web-based, self-report questionnaires administered free of provider and investigator influence.

Baseline characteristics

Important baseline characteristics (e.g., demographics, past healthcare use, COVID-19 impact¹⁹⁰, LBP duration, prior episodes of LBP, visual trajectory questionnaire for pain¹⁸⁶, Quebec Task Force classification of spinal disorders¹³³) will be collected through web-based, self-report questionnaires and the screening provider's medical history and physical exam. Baseline measures included in the NIH research task force's minimum dataset will be collected.⁷³

Primary Outcome Measures

The following primary outcome measures will be collected during the baseline assessment.

- Low back pain impact is defined as a combination of pain intensity, pain interference with normal activities, and functional status, using 9 items of the 29-item PROMIS short form. These items have substantial research support to validate their discriminatory and prognostic importance. Scores on the 9 PROMIS-based items yielding Impact Stratification range from 8 (least impact) to 50 (greatest impact).¹⁹¹
- LBP Intensity: participants will be asked to rate their average LBP over the last week on an ordinal 11-box NRS (0=no LBP, 10=the worst LBP possible). Several studies have shown that ordinal pain scale measures perform as well as the 10-cm Visual Analog Scale (VAS),¹³⁴ a simple, frequently used valid assessment of variation in pain intensity^{119 135} and a reliable measure of treatment efficacy.¹³⁶ The advantage of the 11-box scale over the VAS is that it is easier to administer and score.¹¹⁹

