In consultation with NCCIH program staff and the DSMB in 2022 we have outlined our planned publications for presenting our main results and have revised the primary statistical test that would be used to evaluate differences in mean outcomes across the treatment groups. Specifically, rather than conduct individual tests of SMT alone, SSM alone, and the combination against medical care with adoption of a multiple comparisons correction for three tests we will now use an overall test of equality across the four groups to conduct a single omnibus hypothesis test followed by the estimation of key group comparisons using Fishers least significant difference methods to construct individual nominal 95% confidence intervals with reporting of the induced simultaneous coverage. These methods will be used for primary analysis of the 3 primary effectiveness outcomes : LBP-Impact and pain and disability.

We plan to present principal findings in two key publications. The first publication would focus on average pain and disability over 1-year as the multiple primary outcomes and present recovery at 6-months (previously a primary outcome) as one of the secondary outcomes. A second paper will focus on LBP Impact averaged over months 10-12 as the primary outcome .

Modifications to Statistical Analysis Plan Regarding Primary Outcome

(edited July 2021)

In consultation with the NCCIH program staff and DSMB in the Spring of 2021 we have changed our primary outcome for assessment of treatment impacts on chronicity prevention. Specifically, we have replaced our original NIH Task Force on Research Standards for Chronic LBP (referred to as RTF) dichotomous chronicity measure with the RTF quantitative impact measure. The LBP-Impact outcome measure is a subset of the Promise 29 measures, **which is already being collected at baseline and every month during the follow-up year from the start of the trial**. As a secondary outcome measure, we will compare differences across treatment groups in the distribution of patients with mild, moderate, and severe impact.

Modifications to Statistical Analysis Plan in Response to COVID-19 Impacts

(edited August 2020)

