LBP Impact Effectiveness Hypothesis: SMT alone will decrease the impact of low back pain with at least a moderate effect size of 0.3 standard deviations (Cohen's d). Similarly, SSM alone will decrease the impact of low back pain with at least a moderate effect size of 0.3 standard deviations. The combination SMT+SSM will lead to a stronger but not necessarily additive net reduction compared to the individual component interventions.

Design: As shown in Figure 9.1, we plan to enroll a total of 1000 subjects randomized to one of four treatment groups using a factorial design: medical care (MC); spinal manipulation therapy alone (SMT); supported self-management alone (SSM); and combined SMT+SSM.

LBP Impact Primary Analysis: Our primary analysis will compare each of the treatment groups to MC using an adjusted regression analysis. Specifically, Let Y_{ij} denote the primary outcome variable (average of LBP-Impact over months 10-12) for subject i in site j, and let $Site(2)$ be an indicator variable used to code the two recruitment sites. All analyses will adjust for site and the baseline risk status represented by $RiskGroup$ (0=medium risk; 1=high risk). In order to code the treatment groups we use the variables *SMT-Only* (0=no; 1=only spinal manipulation therapy), *SSM-Only* (0=no; 1=only supported self-management), and *SMT-and-SSM* (0=no, 1=both SMT and SSM). Given interruption by COVID-19 and an associated period of restricted randomization we will also adjust for this modified randomization using the variables *Period(k)* which will be an indicator for: 1=UG3 and UH3 through March 2020; 2=calendar period of restricted randomization; and 3=calendar period of resumed full factorial randomization. We will use an adjusted linear regression model with robust standard error to make inference regarding treatment groups using the following structure where X_{ij} denotes the covariates for subject i:

$$E(Y_{ij} | X_{ij}) = \beta_0 + \beta_1 \cdot Site(2)_j + \beta_2 \cdot RiskGroup_{ij} + \beta_3 \cdot SMT-Only_{ij} + \beta_4 \cdot SSM-Only_{ij} + \beta_5 \cdot SMT-and-SSM_{ij} + \beta_6 \cdot Period(2)_{ij} + \beta_7 \cdot Period(3)_{ij}$$

In the primary regression model the parameters of interest are:

β_3 = adjusted mean difference comparing SMT Only to UMC;

β_4 = adjusted mean difference comparing SSM Only to UMC;

β_5 = adjusted mean difference comparing combined SMT and SSM to UMC.

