Our primary analysis will test the global hypothesis that these three treatment comparisons are all null using a multivariate Wald test with 3 degrees of freedom and alpha=0.05. We will then provide individual confidence intervals for each coefficient that compares an intervention group to medical care based on Fishers least significant difference methods which provide individual nominal 95% confidence intervals and also estimates the simultaneous coverage probability.

Power and Sample Size for Primary Outcome of LBP Impact: To characterize the power of our primary analysis (an overall F-test) we provide a summary table that considers potential standardized mean differences comparing the individual intervention arms to medical care. For a small effect size (Cohen's d of 0.2) and an additive effect we have greater than 90% power to reject the null. However, additivity may not hold so we also consider sub-additive scenarios, and the scenario where only one intervention is effective. For small to moderate effect sizes (0.2 – 0.3 standard deviations) we have >90% with our proposed design. We assume n=1000 enrolled with a realistic 90% follow-up that yields 900 evaluated subjects. We also account for the

imbalanced design due to restricted randomization that will yield approximately 300 subjects in the UMC and SSM alone groups and 200 subjects in each of the SMT and SMT+SSM groups. Power is calculated based on 5,000 simulation replications for each scenario and presented in Table 9.1.

The current design is robust to the enrollment target and follow-up assumptions. For example, with an enrollment of n=1000 subjects and 85% follow-up we would have 90% power for our expected alternative scenario with small treatment effects (0.30 standardized mean difference) that are not additive (sub-additive 1).

A secondary evaluation will consider whether the separate effects of SMT and SSM are potentially additive and this will be done using a formal test for interaction:

$$\text{Interaction Model: } E(Y_{ij} \mid X_{ij}) = \beta_0 + \beta_1 \cdot \text{Site}(2)_j + \beta_2 \cdot \text{RiskGroup}_{ij} + \beta_3 \cdot \text{SMT}_{ij} + \beta_4 \cdot \text{SSM}_{ij} + \beta_5 \cdot \text{SMT}_{ij} \cdot \text{SSM}_{ij} + \beta_6 \cdot \text{Period}(2)_{ij} + \beta_7 \cdot \text{Period}(3)_{ij}$$

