Effectiveness Hypothesis: We will focus on parallel analyses for pain and function. We hypothesize that SMT alone will decrease average pain by at least 1 point, and average disability by 2 points. Similarly, SSM alone will decrease average pain by at least 1 point, and average disability by 2 points, and the combination of SMT+SSM will lead to an sub-additive net decrease of <2 points and <4 points respectively.

Primary outcome variables: We will derive measure of disability and pain by calculating the time-averaged patient outcome using the monthly measurements taken over the year of follow-up.

Primary Analysis: For quantitative outcomes we will focus on analyses that generally do not assume that the effects of SMT and SSM are additive since we have adequate power to evaluate specific group contrasts. We will use linear regression methods with robust standard errors to test for the difference in mean scores comparing each intervention group to MC. Let Y_{ij} denote the outcome of interest (either average pain or average disability for parallel analyses). Similar to our primary analysis of LBP impact 1 we will use a linear regression model with robust standard errors using the structure:

$$\text{Four Groups Model: } E(Y_{ij} | X_{ij}) = \beta_0 + \beta_1 \cdot \text{Site}(2)_j + \beta_2 \cdot \text{RiskGroup}_{ij} + \beta_3 \cdot \text{SMT-Only}_{ij} + \beta_4 \cdot \text{SSM-Only}_{ij} + \beta_5 \cdot \text{SMT-and-SSM}_{ij} + \beta_6 \cdot \text{Period}(2)_{ij} + \beta_7 \cdot \text{Period}(3)_{ij}$$

In the primary regression model the parameters of interest are:

β_3 = adjusted mean difference comparing SMT Only to UMC;

β_4 = adjusted mean difference comparing SMT Only to UMC;

β_5 = adjusted mean difference comparing combined SMT and SSM to UMC.

This model considers each treatment group separately using an indicator of SMT only (*SMT-Only*), an indicator of SSM only (*SSM-Only*), and an indicator of combined therapy with both SMT and SSM (*SMT-and-SSM*). We will also add the baseline outcome as a covariate to perform a variation of ANCOVA for repeated measures.

Table 9.2: Power for the overall F-test of equality of means under various alternative scenarios.

Average pain intensity & disability over 12 months post-randomization (alpha = 0.05/2)

Alternative	SMT Alone	SSM Alone	SMT + SSM	Power
Additive	0.20	0.20	0.40	88%
Sub-Additive 1	0.25	0.25	0.35	85%
Sub-Additive 2	0.30	0.30	0.30	89%
Sub-Additive 3	0.25	0.25	0.25	74%

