Single effect 1a	0	0.30	0.30	96%
Single effect 1b	0.30	0	0.30	88%
Single effect 2a	0	0.25	0.25	83%
Single effect 2b	0.25	0	0.25	71%

Our primary analysis will test the global hypothesis that these three treatment comparisons are all null using a multivariate Wald test with 3 degrees of freedom and alpha=0.05/2 to account for the pair of primary outcomes (pain and disability). We will then provide individual confidence intervals for each coefficient that compares an intervention group to medical care based on Fishers least significant difference methods which provide individual nominal 95% confidence

intervals and also estimates the simultaneous coverage probability.

A secondary evaluation will consider whether the separate effects of SMT and SSM are potentially additive, and this will be done using a formal test for interaction:

$$\text{Interaction Model: } E(Y_{ij} | X_{ij}) = \beta_0 + \beta_1 \cdot \text{Site}(2)_j + \beta_2 \cdot \text{RiskGroup}_{ij} + \beta_3 \cdot \text{SMT}_{ij} + \beta_4 \cdot \text{SSM}_{ij} + \beta_5 \cdot \text{SMT}_{ij} \cdot \text{SSM}_{ij} + \beta_6 \cdot \text{Period}(2)_{ij} + \beta_7 \cdot \text{Period}(3)_{ij}$$

In this model a test of H0: $\beta_5=0$ allows us to determine if there is strong evidence for synergistic or antagonistic effects associated with combined treatment. Given that we evaluate interaction for both disability and pain we will use a Bonferroni corrected alpha of 0.05/2.

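### The LBP-Impact models leave out baseline LBP Impact, which the trial collects and whose counterpart it adjusts for in the pain and disability analysis, at a cost in precision on primary outcome 1

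*Combined protocol and SAP*

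**What the plan says.** **LBP Impact.** In Section 9, LBP Impact Primary Analysis, the plan states "We will use an adjusted linear regression model with robust standard error to make inference regarding treatment groups using the following structure". The displayed model has an intercept, site, risk group, indicators for SMT only, SSM only and the combination, and two period indicators. The secondary LBP-Impact evaluation asks whether the effects are "potentially additive and this will be done using a formal test for interaction", and its equation carries the same adjustment terms. No sentence in the LBP-Impact text adds the baseline value.

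**Pain and disability.** Under Primary Effectiveness Outcome # 2 and 3, the outcome is "either average pain or average disability for parallel analyses" and the displayed four-group equation has the same terms. Below it the plan says: "We will also add the baseline outcome as a covariate to perform a variation of ANCOVA for repeated measures". The matching interaction evaluation ("potentially additive, and this will be done using a formal test for interaction") again prints no baseline term.

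**Availability.** Section 6.2.2 says "The following primary outcome measures will be collected during the baseline assessment", and LBP Impact heads that list. The July 2021 modification in Section 9 describes the Impact measure as one "which is already being collected at baseline and every month during the follow-up year from the start of the trial".

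**The concern.** A programmer who follows the text would adjust primary outcomes 2 and 3 for their baseline values and leave outcome 1 unadjusted. The plan does not say whether this is intended or a sentence that was not repeated. Its own reasoning points towards adjustment: the power sections for chronicity and recovery note that covariates which predict outcome and are unrelated to treatment group improve power.

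Any correlation between baseline and month 10-12 Impact that remains after site, risk group and period is left in the residual variance. Every confidence interval against medical care is then wider than the trial's data allow. The loss matters most where the design has least to spare: the 0.25 SD rows of Table 9.1, lower follow-up, and the interaction test.

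**Working it through.** **Inputs from Section 9.** A 3-df test at alpha 0.05; 1000 enrolled and 90% followed, so 900 evaluated; about 300 each in MC and SSM and 200 each in SMT and SMT+SSM. Multiplying by 0.9 gives 270 / 180 / 270 / 180 for MC / SMT / SSM / SMT+SSM.

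**Assumptions.** The extra 90 evaluated patients in each of MC and SSM belong to the restricted period. Allocation is equal within the two four-arm periods. Residual SD is 1.

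**Noncentrality after period adjustment.** Let a = SSM − MC, b = (SMT+SSM) − SMT, and m = the mean of the two SMT arms minus the mean of the two non-SMT arms. Contrast a uses all 270 + 270 patients. Contrasts b and m use the 180 per arm from the four-arm periods. So

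λ = a²/(2/270) + b²/(2/180) + m²/(1/180) = 135a² + 90b² + 180m².

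- Sub-Additive 3: a = 0.25, b = 0, m = 0.125, so λ = 8.44 + 0 + 2.81 = 11.25.
- Single effect 2b: a = 0, b = 0, m = 0.25, so λ = 11.25.
- Additive: a = b = m = 0.20, so λ = 5.4 + 3.6 + 7.2 = 16.2.

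Power is the noncentral F probability with 3 and 892 df (900 less 8 coefficients).

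**With the baseline covariate.** λ is divided by (1 − ρ²), with 891 error df. Here ρ is the partial correlation of baseline with outcome, given site, risk group and period. The documents give no value, so 0.2 to 0.5 is shown. Power in %:

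| Row | Table 9.1 | Recomputed, no baseline | ρ=0.2 | ρ=0.3 | ρ=0.4 | ρ=0.5 |
|---|---|---|---|---|---|---|
| Additive | 93 | 93.6 | 94.5 | 95.6 | 97.0 | 98.3 |
| Sub-Additive 1 | 91 | 91.3 | 92.4 | 93.8 | 95.5 | 97.3 |
| Sub-Additive 2 | 94 | 93.6 | 94.5 | 95.6 | 97.0 | 98.3 |
| Sub-Additive 3 | 81 | 81.2 | 82.9 | 85.0 | 88.0 | 91.6 |
| Single effect 1a | 98 | 97.6 | 98.1 | 98.6 | 99.1 | 99.6 |
| Single effect 1b | 94 | 93.6 | 94.5 | 95.6 | 97.0 | 98.3 |
| Single effect 2a | 91 | 89.6 | 90.9 | 92.4 | 94.4 | 96.5 |
| Single effect 2b | 80 | 81.2 | 82.9 | 85.0 | 88.0 | 91.6 |

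The no-baseline column reproduces every row of Table 9.1 to within 1.4 points, so the table is consistent with a model that has no baseline term. A simulation with robust Wald tests (2,000 replicates) agrees: for Sub-Additive 3, 82.2% without and 85.4% with baseline at ρ = 0.3, and 82.6% and 91.5% at ρ = 0.5.

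**Confidence intervals.** SMT − MC equals [SMT − ½(MC + SSM)], estimated in the four-arm periods, plus ½a. Its variance is 1/180 + 1/360 + ¼(2/270) = 0.01019, so SE = 0.101 and the 95% half-width is 1.96 × 0.101 = 0.198 SD. The combined arm against MC has the same value. Multiplying by √(1 − ρ²) gives 0.194 / 0.189 / 0.181 / 0.171 SD, which is 2 / 5 / 8 / 13% narrower. Residual variance falls by 4 / 9 / 16 / 25%.

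**Interaction.** Variance = 2/270 + 2/180 = 0.01852, so SE = 0.136 SD. The effect detectable with 80% power is 2.80 × 0.136 = 0.38 SD without baseline, and 0.37 / 0.36 / 0.35 / 0.33 SD with it.

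**Follow-up of 85%.** The plan says that "with an enrollment of n=1000 subjects and 85% follow-up we would have 90% power" for its Sub-Additive 1 case. With all cells multiplied by 0.85/0.90 that row comes to 89.5%, which agrees. Applying 85% to the 0.25 SD rows is an extension made here, not in the plan: Sub-Additive 3 and Single effect 2b fall to 78.7% without baseline and are 80.5 / 82.7 / 85.9 / 89.8% with it. The ρ that offsets a fall from 900 to 850 evaluated patients is √(1 − 850/900) = 0.24.

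**The case against.** The model as printed is a valid pre-specified analysis. It adjusts for both stratification factors and for period, and a further prognostic covariate is an improvement in efficiency, not the repair of an error. That stands.

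The size of the gain rests on an assumed correlation. Entry requires pain of at least 3 and medium or high risk, which narrows the baseline range; risk group is already in the model; and the outcome comes 10 to 12 months later. The partial correlation could be low: at 0.1, Sub-Additive 3 moves only from 81.2% to 81.6%. This stands as a limit on size, not on direction. Risk group is unlikely to absorb the whole gain. If the risk groups differ by 0.5 to 1.2 SD in baseline Impact and 25% to 40% of patients are high risk (both assumed), baseline still removes 7% to 9% of residual variance at an overall correlation of 0.3, and 20% to 24% at 0.5.

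The 0.25 SD rows lie below the hypothesised effect of at least 0.3 SD. In the rows with 0.30 SD effects, power without the covariate is 92% to 97% even at 85% follow-up. The interaction test is secondary, and its detectable LBP-Impact difference is left as an unfilled X, so no stated target is missed. Both points are fair.

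Finally, the printed pain and disability equation also lacks the term that the text below it adds, and the plan calls that analysis similar to the LBP-Impact one. The equations may therefore not be full covariate lists, and adjustment may have been intended throughout. This weakens any inference from the pain and disability interaction equation. It does not settle the LBP-Impact model, for which no sentence supplies the term.

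**Conclusion.** The concern holds. As written, primary outcome 1 is analysed without its baseline value, while the plan adjusts average pain and disability for theirs. The consequence is lost precision only. The randomised comparison stays unbiased, the type I error is unaffected, and Table 9.1 is correct for the stated model. The omission and the direction of the loss are certain for any non-zero partial correlation. The size is not, because it depends on a correlation that the documents do not give. Over the assumed range of 0.2 to 0.5 the 900 evaluated patients would carry the information of about 938 to 1200 (900/(1 − ρ²)). That is a modest gain at the hypothesised effect and a more useful one for the individual intervals, the interaction estimate and the weaker scenarios. The change should be made, but the trial's validity does not depend on it.

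**What to change.** By SAP amendment before unblinding:

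1. Add baseline LBP Impact as a covariate in the LBP-Impact four-group model and in the LBP-Impact interaction model.
2. Write the baseline outcome into the displayed pain and disability four-group equation, where the text already adds it, and into the pain and disability interaction model, so that all primary-outcome models match.
3. State how baseline LBP Impact is scored. Section 6.2.2 says the PROMIS-29 pain-intensity question is collected elsewhere, so the plan should say that the baseline pain NRS supplies that item.
4. State that missing baseline values are handled by the multiple imputation described under General Missing Data Considerations.

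The cost is one covariate per model and a short amendment. The data are already collected, and no patients, visits or forms are added. If the omission was deliberate, the plan should give the reason.

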Table 9.1: Chronicity based on LBP-Impact averaged over months 10-12 of follow-up. Power for the overall F-test of equality of means under various alternative scenarios. (alpha = 0.05)

Alternative	SMT Alone	SSM Alone	SMT + SSM	Power
Additive	0.20	0.20	0.40	93%
Sub-Additive 1	0.25	0.25	0.35	91%
Sub-Additive 2	0.30	0.30	0.30	94%
Sub-Additive 3	0.25	0.25	0.25	81%
Single effect 1a	0	0.30	0.30	98%
Single effect 1b	0.30	0	0.30	94%
Single effect 2a	0	0.25	0.25	91%
Single effect 2b	0.25	0	0.25	80%

In this model a test of $H_0: \beta_5=0$ allows us to determine if there is strong evidence for synergistic or antagonistic effects associated with combined treatment.

Secondary Effectiveness Outcome of Chronicity: Chronic back pain: For a subject to be classified as a chronic back pain patient at the 1-year assessment they must endorse having “a back pain problem that has persisted at least 3 months and has resulted in pain on at least half of the days in the past 6 months”. This outcome is based on specific items

from the NIH Research Task Force recommended minimal data set:⁷³ Question 1 on LBP duration; and Question 2 on the proportion of days that LBP has been a problem in the past 6 months. To evaluate chronic back pain we will consider the 1-year status as a key secondary outcome for chronicity prevention, and will use the 6-month status as another key secondary outcome.

Chronicity Hypothesis: SMT alone will decrease the rate of cLBP by 6-9% from a baseline MC level anticipated to be 20% or higher. Similarly, SSM alone will decrease the rate of cLBP by 6-9%, and the combination of SMT+SSM will lead to an additive net reduction.

Secondary Chronicity outcome Analysis: The analysis of the secondary binary outcome will use parallel marginalized tests of the average SMT treatment effect and the average SSM treatment

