likelihood ratio test of one treatment modality (either SMT or SSM). For simulations we considered crude analysis while our formal analysis will additionally adjust for site and baseline risk and therefore improve power since these are variables that only predict outcome and are not related to treatment group. For each scenario we simulated 5,000 data sets and empirically calculated power as the percentage of replicates in which the null hypothesis was rejected.

Using simulations with n=1000 subjects, 90% follow-up, and accounting for our imbalanced allocation due to COVID interruption we compute power for analyses that consider individual marginal treatment effects for both SMT and SSM. If we assume a UMC chronicity rate of 20% and a relative risk of 0.65 (rate under treatment = $20\% * 0.65 = 13\%$, or an absolute risk reduction of 7%) then we have >85% power to detect average SSM or SMT effects. If we a smaller effect corresponding to a relative risk of 0.70 (rate under treatment = $20\% * 0.70 = 13\%$, or an absolute risk reduction of 7%) then we have approximately 70% power to detect average SSM or SMT effects of this magnitude (specifically accounting for imbalance power is 72% for SSM and 70% for SMT). Power is greater for any relative risk when the UMC rate is increased to 30% or 40%. These relative risk effect sizes equate to medium effect sizes and are considered clinically important by Cochrane's Back Review Group.¹⁴⁸ We have not powered the study to detect interaction for the binary chronicity endpoint, but rather have powered the study to detect interaction on the underlying function and disability scales (see below).

Furthermore, we have excellent power to detect interaction effects where the effect of SMT and SSM may be synergistic or antagonistic, and using alpha=0.05 we have >80% to detect a X-point difference in LBP Impact treatment effects of one modality across the strata defined by the other treatment modality.

Secondary Effectiveness Outcome of Recovery: Determine the effectiveness of SMT, SSM, and the combination of SMT+SSM relative to medical care (UMC) in promoting recovery from acute or subacute LBP at 6 months.

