Power and Sample Size for primary effectiveness outcomes # 2 and # 3: See Table 9.2. We will conduct longitudinal analysis of the underlying RMDQ and Pain NRS scores. Specifically, we will conduct analyses using the mean area under the curve for both disability and pain and use linear regression to evaluate treatment effects on the native underlying scales. With n=1000 subjects evaluated through one year and using alpha=0.05/2 for the two outcomes and an overall F-test we have >80% power across a range of scenarios presented in the table below. To orient standardized effects a marginal 2-point mean difference on RMDQ for any treatment modality compared to UMC assuming a standard deviation of 6.5 or less,^{149 153} corresponds to a Cohen's D of $2.0/6.5 = 0.31$, and >80% power to detect a marginal 1-point difference on Pain NRS assuming a standard deviation of 3.0 or less corresponds to a standardized effect of 0.33.^{149 153} Note that our outcome is the area under the curve through 12 months, which is a patient-level weighted average, and the standard deviation (SD) for this outcome will be less than the SD for a single measurement. Our power calculations are conservative since we use the SD for a single measurement. Although we have <80% power if SMT and SSM have small marginal effects of 0.25 SD and no additional benefit when combined (sub-additive 3 below) this scenario leads to no single treatment arm yielding an effect of 2 points on RMDQ (0.31 SD) or 1 point on Pain NRS (0.33 SD) and therefore suggests our design is appropriate for important and plausible effect sizes and not overpowered for effects that may not be meaningful.

Furthermore, we have excellent power to detect interaction effects where the effect of SMT and SSM may be synergistic or antagonistic, and using alpha=0.05/2 we have >80% to detect a 2.7-point difference in disability or 1.3-point difference in pain treatment effects of one modality across the strata defined by the other treatment modality.

Secondary Analyses of the 3 primary effectiveness outcomes and other secondary outcomes: We will conduct a number of pre-specified secondary analyses.

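### The text claims more than 90% power for LBP Impact at 0.2–0.3 SD, but two 0.25 SD rows of Table 9.1 show 81% and 80%, and no non-additive 0.20 SD case is tabled

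*Combined protocol and SAP*

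**What the plan says.** All of this is in Section 9 of the combined protocol and SAP. Effects are written below as SMT alone / SSM alone / SMT+SSM, each against medical care (MC), in SD units.

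- **Power and Sample Size for Primary Outcome of LBP Impact.** The text first gives power above 90% for an effect of 0.2 with additivity. It continues: "However, additivity may not hold so we also consider sub-additive scenarios, and the scenario where only one intervention is effective". The next sentence is "For small to moderate effect sizes (0.2 – 0.3 standard deviations) we have >90% with our proposed design". The assumptions are 1000 enrolled, 90% follow-up (900 evaluated), and about 300 patients in each of MC and SSM and 200 in each of SMT and SMT+SSM.
- **Table 9.1**, headed "Power for the overall F-test of equality of means under various alternative scenarios. (alpha = 0.05"). Two of its eight rows are below 90%: Sub-Additive 3 (0.25/0.25/0.25) at 81% and Single effect 2b (0.25/0/0.25) at 80%.
- **The 85% follow-up example** in the same subsection: "we would have 90% power for our expected alternative scenario with small treatment effects (0.30 standardized mean difference) that are not additive (sub-additive 1"). Table 9.1 defines Sub-Additive 1 as 0.25/0.25/0.35; the row 0.30/0.30/0.30 is Sub-Additive 2.
- **LBP Impact Effectiveness Hypothesis.** Each single treatment is expected to have "at least a moderate effect size of 0.3 standard deviations".
- **Interaction for LBP Impact**, placed under the power text for the secondary chronicity outcome: "we have >80% to detect a X-point difference in LBP Impact treatment effects of one modality". The matching sentence for outcomes 2 and 3 is complete: "we have >80% to detect a 2.7-point difference in disability or 1.3-point difference in pain treatment effects".

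**The concern.** The additive case is dealt with before the disputed sentence, and the sentence in between brings in the non-additive scenarios. The claim of more than 90% therefore reads as covering those scenarios over the whole range from 0.2 to 0.3 SD. Two tabled scenarios inside that range miss it by 9 to 10 points, and at 0.20 SD the table holds no non-additive scenario at all.

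This is the power statement for a primary test, and Section 9 justifies the cut from 1180 to 1000 by an evaluation of power for LBP Impact and the other primary outcomes. If the omnibus test turns out null, someone relying on the sentence would take a true 0.25 SD effect to have had less than a 10% chance of being missed. The table puts that chance at 19–20% for two patterns. The 85% example is offered as evidence of robustness, so the reader needs to know which scenario it describes. The interaction claim cannot be checked while its number is missing.

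**Working it through.** **Inputs from Section 9.** Global test with 3 df, alpha 0.05; 900 evaluated; arms 300/200/300/200 (MC/SMT/SSM/both) × 0.9 = 270/180/270/180; period indicators in the analysis model.

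**Assumption.** The surplus MC and SSM patients (100 each enrolled, 90 each evaluated) form the restricted-randomization period, and the power model adjusts for period. The plan specifies period adjustment for the analysis but does not say whether Table 9.1 used it, so both versions are shown.

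**Formula.** Power = P(F′ > F crit), where F′ is noncentral F with 3 numerator df and noncentrality λ, and F crit is about 2.615. With period adjustment, λ = 180 × (sum of squares of the four arm means about their mean) + 90 × (the same for MC and SSM only). Without it, λ is the sample-size-weighted sum of squares over the four arms.

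- Sub-Additive 3: mean 0.1875, sum of squares 0.1875² + 3 × 0.0625² = 0.046875. λ = 180 × 0.046875 + 90 × (2 × 0.125²) = 8.4375 + 2.8125 = 11.25.
- Single effect 2b: sum of squares 4 × 0.125² = 0.0625; MC and SSM do not differ. λ = 180 × 0.0625 = 11.25.

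**Reproducing Table 9.1.**

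| Scenario | Effects | Stated | λ (adjusted) | Adjusted | Unadjusted |
|---|---|---|---|---|---|
| Additive | 0.20/0.20/0.40 | 93% | 16.20 | 93.6% | 95.5% |
| Sub-Additive 1 | 0.25/0.25/0.35 | 91% | 14.85 | 91.3% | 93.2% |
| Sub-Additive 2 | 0.30/0.30/0.30 | 94% | 16.20 | 93.6% | 94.7% |
| Sub-Additive 3 | 0.25/0.25/0.25 | 81% | 11.25 | 81.2% | 83.2% |
| Single effect 1a | 0/0.30/0.30 | 98% | 20.25 | 97.6% | 97.6% |
| Single effect 1b | 0.30/0/0.30 | 94% | 16.20 | 93.6% | 97.1% |
| Single effect 2a | 0/0.25/0.25 | 91% | 14.06 | 89.6% | 89.6% |
| Single effect 2b | 0.25/0/0.25 | 80% | 11.25 | 81.2% | 88.3% |

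The adjusted model matches every row within 2 points (largest gap 1.4, Single effect 2a). A simulation of the same model with 20,000 replicates gave 81.0% for Sub-Additive 3 and 81.3% for Single effect 2b. Both rows are below 90% with or without adjustment.

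**Patterns at 0.20 SD that the table omits**, adjusted (unadjusted): 0.20/0.20/0.20, λ = 7.2, 60.1% (62.5%); 0.20/0/0.20, λ = 7.2, 60.1% (68.9%); 0/0.20/0.20, λ = 9.0, 70.9% (70.9%).

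**The 85% follow-up example** (850 evaluated), adjusted (unadjusted): 0.25/0.25/0.35, λ = 14.03, 89.5% (91.7%); 0.30/0.30/0.30, λ = 15.30, 92.1% (93.4%). The stated figure is 90%.

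**The missing interaction figure.** SE = √(2/270 + 2/180) = 0.136 SD. Detectable difference at 80% power and alpha 0.05 = 0.136 × (1.960 + 0.842) = 0.38 SD. As a check, alpha 0.05/2 gives 0.420 SD: × 6.5 = 2.73 RMDQ points and × 3.0 = 1.26 NRS points, against the plan's 2.7 and 1.3. The documents give no SD for LBP Impact. If it were 7 to 10 points (an assumption), the missing figure would be about 2.7 to 3.8 points.

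**The case against.** **The correct table follows at once.** Nothing is hidden, no tabled power is below 80%, and the sentence can be seen as a loose summary. All of that stands, and it makes this a correction of text, not of design. It does not make the sentence true.

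**A reader might infer that 1000 is too few.** The documents do not support that. Each tabled scenario has at least 80% power at the assumed 90% follow-up. The hypothesis is 0.3 SD for each single treatment with a stronger combination. That is not a tabled row, but the flat 0.30 row already has 94%, and 0.30/0.30/0.40 recalculates to 97.6% (λ = 20.25).

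**A reader might infer that 0.30 is the slip in the 85% example,** because 89.5% is closer to 90% than 92.1% is. That is not established. The hypothesis is itself 0.3 SD, which favours the label as the slip. Both recalculated values lie near 90%, and the preference depends on a period adjustment that the plan does not state for its power figures; without it, 0.25/0.25/0.35 gives 91.7%. The value 0.30 could also be the midpoint of 0.25 and 0.35, though the text does not say so.

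**A reader might infer that any departure from additivity at 0.20 SD costs much power.** It does not. With period adjustment, 0.20/0.20/0.50 gives 99.3% and 0.20/0.20/0.38 gives 91.2%. Stronger sub-additivity (0.20/0.20/0.30, 77.5%), a flat pattern or a single effect is what lowers it.

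**The pain and disability text is a weak precedent.** It does say "Although we have <80% power if SMT and SSM have small marginal effects of 0.25 SD and no additional benefit when combined", but there the tabled power is 74%, below a threshold that no Table 9.1 row crosses. That text also passes over its own 71% row.

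**Conclusion.** The concern holds as a mismatch between text and table. The claim of more than 90% over 0.2–0.3 SD is contradicted by two of the eight rows of Table 9.1, at 81% and 80%, and has no tabled support at 0.20 SD unless effects are additive. This conclusion needs only the plan's own table. The recalculation adds that the table, not the sentence, is right.

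The 60–71% for flat or single-effect patterns at 0.20 SD comes from scenarios that the plan did not set itself, and shows only why the low end of the range should not be claimed. The 85% example is internally inconsistent, but the documents do not settle which element is wrong. The unfilled interaction figure is a minor gap in a secondary evaluation. Its value of about 0.38 SD rests on the 900-patient allocation and a normal approximation.

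Table 9.1, the test, the alpha and the sample size are not disputed.

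**What to change.** 1. Replace the sentence with: *Across the scenarios in Table 9.1, power is 93% at 0.20 SD with additive effects, 80–91% in the 0.25 SD scenarios and 94–98% in the 0.30 SD scenarios; non-additive 0.20 SD scenarios were not evaluated.* Alternatively, add such rows from the trial's own simulation. In either case, state whether the simulation adjusts for period.
2. Have the sponsor confirm from its simulation which scenario the 85% follow-up example describes, and make the effect size, label and power agree with Table 9.1.
3. Replace the X with the detectable LBP Impact interaction (about 0.38 SD at alpha 0.05 and 80% power), converted to points with a stated SD for LBP Impact, or delete the claim.

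The cost is SAP wording, a check of existing simulation output and, only if rows are added, a short rerun. Design, tests, alpha, sample size and data collection are unaffected.
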